#### **C.17.a. Semi-Structured Qualitative Interviews.**

To better understand both the specific intervention components that may impact outcomes and potential issues in implementation, we may utilize semi-structured interview methods to study implementation processes. Our sample will consist of the study interventionists (pharmacist, RN, LPN), a sample of approximately 5-10 Durham VAMC PCPs, which may include providers at Durham affiliated community-based clinics, (depending on data saturation) [to examine issues involved in future implementation], and a sample of approximately 15-25 patients (depending on data saturation) who were in the intervention group. To better understand differences in attributes of the intervention that may impact implementation in parent medical centers and community outpatient clinics, we will seek patients who have primary care providers at both the Durham VAMC/Hillandale clinics (i.e. parent VAMC) and in Durham affiliated community based clinics (primarily Greenville, where we actively physically enrolled patients in the study). Our goal is that patients that have had a variety of experience with the titration process. For example, this may include: 1) patients who started and remained at the level 2 (pharmacist delivered) resource intensity level, 2) patients who started at the level 2 (pharmacist delivered) resource intensity level and were down stepped to another intensity at some time during the study, 3) patients who started and remained at the level 1 (RN delivered) resource intensity level; 4) patients who started at the level 1 (RN delivered) resource intensity level and were down stepped to another intensity at some point during the study and; 5) patients who started at the level 1 (RN delivered) resource intensity level and were up stepped to another intensity at some point during the study. The staff

interviews will be guided by an implementation framework developed by Weiner. The framework suggests that implementation is a function of the clinics' readiness for change, the quality of the implementation policies and practices, climate for implementation, extent to which intended users of the innovation perceive that innovation use fosters the fulfillment of their values, and extent to which the innovation fits with task requirements. Patient interviews will be designed to examine perceptions of intervention effectiveness based on domains of the Chronic Care Model that are observable by patients: patient activation, delivery system design, goal setting/tailoring, problem solving, and follow-up/coordination.

**C.17.a.1. Interview Procedures.** The following procedures will be followed for interviews for staff members.

1. Interviews will only be conducted by research study team staff of the Durham VA Medical Center Health Services Research & Development Center of Excellence.
2. Study interventionists and Durham VAMC PCP's interviews will be conducted over the telephone. A waiver of documentation of informed consent is being requested. However, a staff member may request an in person interview if he or she prefers.
3. Interviews of the patients will also be conducted either by telephone or in person.
4. Patients will have already gone through an informed consent process and signed VA form 10-3203 prior to participating in the interviews.
5. **Staff contact** information will be obtained through VA Outlook and/or the VA phone book on the VHA intranet
6. **Patient Contact information** will be obtained from study records and/or the VHA electronic health record.
7. **Selected PCP's and staff interventionists** will be contacted via email using the attached text.
8. **Selected PCP's and staff interventionists** may decline to participate (opt-out) upon receiving the email.
9. **Selected PCPs and staff interventionists** may write back to schedule a time to talk that meets within their schedule. We will make clear that our interview does not supersede any work events that may arise and can be interrupted and resumed later if necessary.
10. If the **selected PCP or staff interventionist** does not respond to the email, study staff will call the staff member using the attached telephone script.
11. The telephone script for **Selected PCPs and staff interventionists** contains the elements of informed consent. A waiver of documentation of informed consent is being requested from the IRB. [Waiver of Documentation of Informed Consent for interventionist/providers approved August 24, 2011]
12. **Staff members** may decline to participate at any point.
13. **Patients** may decline to participate at any point.
14. Interviews will be conducted using a semi-structured interview guide. This guide will be sent to the IRB before it is used. **No interviews will be conducted until the IRB has approved the structured interview guides.**
15. **There will be no exclusions based on staff member race, ethnicity, or gender.**

**C.17.a.2. Additional Procedures to Protect Confidentiality of Employees.** The following additional procedures will be followed to provide additional protection of employee confidentiality.

1. PCP supervisors will not be told whether or not an individual has agreed to participate in an interview.
2. PCP supervisors will not be told whether or not an individual has participated in an interview.
3. As with all studies, there will be no sharing individual responses to interviews with individuals not on the study staff list on file with the Durham VAMC IRB.
4. All names will be redacted from final transcripts of interviews that will be used for qualitative analysis
5. As described in section on data handling, extensive efforts are being made to maintain the security of data.
6. An experienced staff member who had not previously been involved in this study will be asked to complete the interviews of the study interventionists.

### **C.18. Primary Outcome – Blood Pressure**

Continuous change in systolic blood pressure will be measured as the primary outcome. BP will be measured at baseline and at the 6-, 12-, and 18- month study visits. At each study visit, three measures will be obtained. The final outcome will be the average of the three measures. All BP measurements will be performed using electronic blood pressure cuffs, which have been shown to be equivalent to (and ecologically safer than) the gold standard of random zero sphygmomanometers. Study personnel will be trained and certified in correct measurement technique using established methods. These are currently the methods that a Co-I of the proposed study ([name]) is using in his currently funded NHLBI trial. In addition to blood pressure, pulse will also be measured.

Systolic BP has been chosen as the primary outcome because it is far more likely to be out of control than diastolic BP. Fewer than 2% of patients with HTN on medications have isolated poor diastolic BP control.

We are proposing examining systolic BP as the primary outcome, as opposed to changes in control, because equal incremental improvements lead to greater reduction in complications at the higher end of the scale (i.e. higher BP). That is, there is a greater health impact in lowering someone's SBP from 160 to 150 mmHg than there is from lowering it from 145 to 135, even though the latter crosses a threshold and brings the patient "under control." As argued for HbA1c for Pogach et al. (2006), we therefore felt that continuous SBP was a more clinically relevant primary outcome than control, given that patients lowered from 160 to 150 would be considered "failures" using the latter, dichotomous outcome. Extensive epidemiological data have confirmed the importance of SBP as a primary determinant of risk. The relationship between BP and CVD risk is relatively continuous and SBP reductions of 6 mmHg translate to reduction in clinical events and all-cause mortality.

Study visits may occur during a time period encompassing plus or minus two months around the intended study visit. In other words, the 6 month study visit may occur between 4 and 8 months following the initiation of study procedures. The 12 month study visit may occur between 10 and 14 months following the initiation of study procedures. The 18 month study visit may occur between 16 and 20 months following the initiation of study procedures.

### **C.19. Safety Parameters for Primary Outcome**

Certain extreme BP values, both high and low, carry an urgent risk of major complication. As a result, if the most recent BP measurement is reported during a patient phone call, at a study data collection visit, or during other contact between study clinical staff and a patient is at one of these extremes, we will advise patients to take specific actions to minimize those risks. For SBP  $\geq$  180 mmHg or DBP  $\geq$  110mmHg, we will advise the patient to contact her/his triage nurse (or other similar position) within 24-48 hours. If a patient is advised to contact the triage nurse, a note will be placed in the patient's medical record. For participants that have moved care to a different VA facility (as described in section C.3.b) we will advise patient to go to the emergency room or urgent care facility but not put a note that requires PCP co-signature in their medical record (because it is not possible to require co-signatures of providers from another facility). This level corresponds to JNC 7

classification of Stage 3 hypertension and are the safety criteria currently used by our data safety monitoring board in TCYB and TEACH-DM. For SBP  $\geq$  210 mmHg or DBP  $\geq$  120 mmHg, or SBP  $\leq$  90 mmHg and/or DBP  $\leq$  40, we will advise the patient to seek immediate care. For all instances in which we recommend seeking immediate care, we will put a note that requires PCP co-signature in the patient's medical record. For participants that have moved care to a different VA facility (as described in section C.3.b) we will advise patient to go to the emergency room or urgent care facility but not put a note that requires PCP co-signature in their medical record (because it is not possible to require co-signatures of providers from another facility).

## **C.20. Secondary Outcomes**

### **C.20.a. Systolic Blood Pressure Control.**

As a secondary analysis, we will examine the difference in the degree of systolic BP control over the 18 months of the study between the intervention and control arms. Control will be defined as SBP  $\leq$  130mmHg for hypertensive patients with diabetes and  $\leq$  140mmHg for patients without diabetes.

### **C.20.b. Intervention Cost Measurement**

We will assess intervention-related costs and resource-utilization costs to create a complete picture of the costs that would be incurred if the intervention were adopted system-wide. We will examine outcomes over 18 months, matching the timing of the measurement of the primary outcome. Intervention costs include labor and capital costs. Labor will include interventionist time, assessed using VA Human Resources data for salaries and carefully tracked study data on time spent per task. LPN, RN and PharmD time on calls, clinic time devoted to the study, and training costs to implement the study will all be included at the relevant wage and fringe benefit rates. We do not anticipate that the interventions will place additional time burden on physicians. We will assume that capital costs such as overhead costs, office space and supply costs, and telephone services costs will be neutral because implementation would use existing capitol. In addition, equipment costs of the electronic home BP monitoring units (and batteries) will be included, using current market prices.

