If a patient does not come in for a 6 or 12 month study visit, titration may occur based on the above protocol without having study visit BP measurements. If no BP measurements are available, the patient will continue at the same intensity level. The study physician ([name] or his appropriately licensed back-up/replacement, which may include a mid-level provider) must approve any changes in intensity level for patients who do not have 6 or 12 month study BP measurements. If the study physician does not believe there is sufficient BP information to make a change for patients without a 6 or 12 month study visit, no changes in intensity level will be made.

Study visits may occur during a time period encompassing plus or minus two months around the intended study visit. In other words, the 6 month study visit may occur between 4 and 8 months following the initiation of study procedures. The 12 month study visit may occur between 10 and 14 months following the initiation of study procedures. The 18 month study visit may occur between 16 and 20 months following the initiation of study procedures.

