#### **C.9.c. Rules for Automatically Titrating Intervention Patients up to High Clinical Intensity.**

If a patient reaches either of the three rules below, either at a study visit or between study visits, for close parallel to real world clinical decision-making the patient is immediately escalated to the highest level of care. If a patient is titrated to the highest level between study visits, then they must remain at the highest intensity level for at least 6 months (for example, if a patient is up stepped at month 3, they will not be reevaluated for possible down stepping until month 12).

- Mean of home systolic BPs reported during a study behavioral call  $\geq 160$  mmHg
  - This automatic increase in resource intensity will not include adding 5 mmHg to home systolic BP measurements. A minimum of 4 blood pressure readings considered to be validly reported by the appropriately licensed clinical interventionist will be required for automatic titrating of the intervention patients to the high clinical intensity level. Any exception to the required number would need to be approved by the study physician or an appropriately licensed clinical backup.
- Hospitalization due to stroke and/or MI. Patient will be asked at intervention phone calls if they have been hospitalized for stroke, MI and/or heart attack, we will report answers based on patient self report and/or indication of hospitalization in VA electronic health record.
- A patient triggers the safety protocol for blood pressure based on a blood pressure (see section C.19 for safety criteria) measurement considered to be valid by the appropriately licensed clinical study staff member.

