### **C. 13. Intervention Component – Pharmacist-Directed Algorithmic Medication Management [high/level 2 resource intensity]**

Many patients require medication intensification to achieve targets for BP. Appropriate medication management requires accurate and timely information on the patient's current level of disease control, treatment adherence, evidence-based recommendations, and potential barriers to successful implementation. Patients who meet criteria for high/level 2 resource intensity disease management will receive medication management from a clinical pharmacist, who will be backed up by an MD ([name] or his appropriately licensed back-up/replacement who could be a mid-level provider). Pharmacists are authorized to make medication changes according to accepted treatment algorithms and based on their scope of practice. Via CPRS, the pharmacist will also communicate these changes to the patient's PCP. While pharmacists may collaborate with the patients' providers when clinically indicated, they do not have to rely on providers to make the changes. The goal of the medication component of the intervention is not to replace clinic based management, but rather to supplement it based on home BP readings in order to more efficiently implement interventions that may otherwise be left until the next provider appointment. The pharmacist will attempt to contact patients every month while they are in the high-intensity titration level of the intervention. At the pharmacist's discretion, patients may be asked to come to the Durham VAMC for an in-person meeting, however, most interactions will be conducted over the phone. During each encounter, the pharmacist will have information from both CPRS and the behavioral-telephone calls conducted as part of the intervention so information on such topics as patient medication and barriers to adherence can be available. During the initial encounter the pharmacist will assess the patient's medication adherence, review all BP related medications, discuss the purpose of each medication, and the appropriate administration of each medication. While not explicitly planned, the pharmacist (or appropriately licensed clinical backup) may discuss other medicines if he or she feels that this is needed to appropriately manage BP medication. At subsequent contacts the pharmacist will review any medication changes with the patients and update patients' medication lists. All calls will be indicated with a note in the Durham VAMC electronic health record.

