
For patients who require a change in their prescription, the pharmacist will communicate the change to the VA pharmacy and the patient's PCP using standard clinic procedures. At the next monthly telephone contact, the pharmacist will assess any new symptoms (e.g., hypotension). This will allow adequate time for the patient to obtain the medication and to get accustomed to the medication change. Any medication change that requires additional testing or follow-up (e.g., assessment of serum potassium, sodium and creatinine following the addition of an ACE-I or diuretic) will be ordered and followed-up. In cases where a medication change is made, a note will be generated for the patient's medical record and co-signed by the patient's PCP. This algorithm and methods of communication of changes to the PCP and follow-up of required labs has all been developed and tested in the HINTS study. If any significant adverse events occur, the pharmacist will consult with the patients' provider along with the study physician ([name] or his appropriately licensed back-up/replacement who could be a mid-level provider or other appropriate clinician) to take appropriate action and/or make further recommendations. Patients will also be provided with a toll-free number to call the pharmacist to report any adverse events or ask questions. All medication changes will be indicated with a note in the Durham VAMC electronic health record. Medications algorithms are being submitted separately to the Durham VAMC IRB. [approved by IRB on August 24, 2011]

Because this is a pragmatic clinical trial, it is expected that patients may not be able to be contacted or miss some portion of the scheduled telephone calls or other contacts with study personnel.

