#### **C.15. Measuring Components and Fidelity of the Intervention.**

At each intervention encounter, the interventionists (i.e. nurse or pharmacist) will review a checklist of issues pertinent to that particular patient. The checklist will be maintained in the intervention database, which the interventionist will use while s/he is conducting intervention calls. The database will facilitate ascertainment of compliance with this intervention.

All telephone calls initiated by the interventionist will be conducted while s/he is logged on to the intervention database created for the study. This will record the number and duration of calls and the type of intervention components delivered for each patient that will be used for cost analyses. The database will also contain a standardized script. In the intervention software, the interventionists will maintain a log for calls initiated by patients and calls to providers. Further, a log of all consultations by study interventionists/clinicians on patient clinical issues will be maintained in the intervention software. This includes any contacts with a patient's PCP. All pharmacist-made medication changes will be recorded in the intervention software (in addition to CPRS). The project coordinator will review all logs weekly to assure that the components that were due at the scheduled call were in fact recorded as delivered. Drs. [name] and [name] (or his appropriately licensed back-up/replacement) will meet with the interventionists approximately monthly to discuss any possible problems with the scheduled delivery of the intervention. A member of the unblinded study team will listen to approximately 1 phone call approximately every 2 weeks to ensure that what is being recorded in the databases is actually being covered on the calls. The process may become less frequent if consistent quality is observed. In addition, more phone calls may be listened to if necessary to ensure quality.

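### The costing section anticipates no added physician time, but the titration and medication-management sections create physician tasks only in the intervention arm, so the ICER is probably understated by an unknown and possibly small amount

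*Protocol*

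**What the plan says.** C.20.b sets the aim of the costing: "to create a complete picture of the costs that would be incurred if the intervention were adopted system-wide". For labour it says "LPN, RN and PharmD time on calls, clinic time devoted to the study, and training costs to implement the study will all be included". Staff pay is to be valued with benefits. The next sentence is "We do not anticipate that the interventions will place additional time burden on physicians".

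Other sections give physicians work:

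- **C.13, medication changes (level 2):** "a note will be generated for the patient's medical record and co-signed by the patient's PCP".
- **C.13, back-up (level 2):** patients "will receive medication management from a clinical pharmacist, who will be backed up by an MD". The replacement may be a mid-level provider.
- **C.13, significant adverse events:** the pharmacist consults both the patient's provider and the study physician.
- **C.9.b, planned titration:** the study physician, or a replacement who may be mid-level, "must approve any changes in intensity level for patients who do not have 6 or 12 month study BP measurements".
- **C.9.c, automatic up-titration (minimum number of home readings):** "Any exception to the required number would need to be approved by the study physician or an appropriately licensed clinical backup".

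On records, C.15 says that "a log of all consultations by study interventionists/clinicians on patient clinical issues will be maintained in the intervention software", including contacts with the PCP, and that pharmacist medication changes are recorded there too. Number and duration are promised for calls, for use in the cost analyses. No duration is mentioned for consultations, PCP contacts or co-signatures.

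D.6.b defines the ICER as the between-arm difference in average cost divided by the between-arm difference in average SBP reduction. If resource utilization does not differ between arms, only intervention costs enter it.

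**The concern.** The costing is meant to describe adoption across the VA, and cost-effectiveness is a stated secondary hypothesis (H3, A.1.c). C.20.b rests on a premise that the protocol's own procedures contradict. The omitted cost also differs by arm: the tasks in C.9.b, C.9.c and C.13 come with titration and level 2 care, and control patients get only booster-level LPN calls (C.16). An omitted cost common to both arms would cancel from the ICER numerator. One that falls mainly on the intervention arm does not.

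**Working it through.** The protocol states no ICER, no physician minutes and no physician wage, so there is no figure to reproduce. The check has three steps.

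**1. Which arm generates each task**

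| Task | Section | Intervention | Control |
|---|---|---|---|
| PCP co-signs medication-change note | C.13 | level 2 | no |
| MD or mid-level back-up of pharmacist | C.13 | level 2 | no |
| Provider and study-physician consultation on significant adverse events under medication management | C.13 | level 2 | no |
| Approval of level change without study BP | C.9.b | yes | no |
| Approval of exception to reading count | C.9.c | yes | no |
| PCP co-signs note for extreme BP | C.19 | yes | yes |
| Possible study-physician help to LPN at booster level | C.10.a.2, C.16 | yes | yes |

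Five tasks belong to the intervention arm alone and two can arise in both. Table 2 expects about 70 of 200 intervention patients at level 2 at baseline.

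The utilization data do not fill the gap. C.20.c counts outpatient encounters by clinic stop code and is not described as capturing co-signatures, back-up or approvals. Primary care visits that are saved would therefore count as savings, while physician input to level 2 care would not count as a cost.

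**2. Direction**

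ICER = (C_int − C_ctl) / (R_int − R_ctl), where C is average cost and R is average mmHg reduction.

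If physician costs p_int and p_ctl are left out, the ICER changes by −(p_int − p_ctl) / (R_int − R_ctl). With a positive SBP difference this lowers the ICER whenever p_int exceeds p_ctl. Here p_int is net: time added by the tasks above, minus PCP work outside visits that the pharmacist replaces.

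**3. Size, by assumption only**

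The denominator is the 5 mmHg design difference in D.3. All minutes, wages and numbers of medication changes below are assumptions; none comes from the protocol.

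*Co-signatures alone*, assuming 2 to 6 changes per level 2 patient, 2 to 5 minutes each and USD 90 to 150 per hour:

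- Low: 2 × 2/60 × 90 = USD 6 per level 2 patient.
- High: 6 × 5/60 × 150 = USD 75 per level 2 patient.
- Per intervention patient, × 70/200 = 0.35: USD 2.10 to 26.25.
- Per mmHg, ÷ 5: USD 0.42 to 5.25.

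The 0.35 is the expected baseline split. Levels change later, so it is only a rough weight.

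*All physician tasks*, as net minutes per intervention patient over 18 months:

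| Net minutes | USD per hour | USD per patient | USD per mmHg (÷ 5) |
|---|---|---|---|
| 5 | 75 | 5/60 × 75 = 6.25 | 1.25 |
| 15 | 75 | 15/60 × 75 = 18.75 | 3.75 |
| 30 | 150 | 30/60 × 150 = 75 | 15 |
| 120 | 150 | 120/60 × 150 = 300 | 60 |

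The spread from USD 1.25 to 60 per mmHg shows how little the documents fix the size.

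**The case against.** The strongest case against the point has four parts.

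- **The sentence is a forecast, not an exclusion.** Nothing in C.20.b forbids costing physician time that does arise, and its clinic-time item is undefined. A reader might infer that physician time is formally excluded; the text does not go that far. It remains true that the labour list names no physician time and that the forecast contradicts required procedures.
- **The work may be replaced, not added.** C.13 says pharmacists need not rely on providers to make changes, and that the component brings forward action which might otherwise wait for the next appointment. A co-signature could displace PCP work. This stands as an offset of unknown size, and it is why the direction is probable, not proven. Co-signature is still unlikely to take no time: B.7.c reports that PCPs overrode fewer than 5% of medication changes in HINTS, which suggests they looked at them.
- **Many tasks are conditional or need not fall to a physician.** The approvals cover only level changes without study BP and exceptions to the reading count. A mid-level or other licensed back-up may act, and adverse-event consultation applies only to significant events. The C.9.b approval, triggered by missing study BP, is arguably a trial cost and not an adoption cost. This supports a small effect. Mid-level time is not listed either, however, and co-signature applies to every medication change.
- **No conclusion is shown to change.** Neither A.1.c nor D.6.b states a cost-effectiveness threshold, and the analysis is secondary. This stands, and it keeps the point minor.

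**Conclusion.** The point holds as an internal contradiction with a probable direction. Followed as written, C.20.b leaves out a cost that falls mainly on the intervention arm, which probably understates the between-arm cost difference and the ICER. If utilization does not differ, D.6.b puts intervention cost alone in the numerator and the omission passes through in full.

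The direction assumes that added physician time exceeds the PCP work replaced outside visits, and that the intervention lowers SBP more than control. The size cannot be determined from the documents and may be small.

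Three stronger readings are not supported:

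- **That a bias in the intervention's favour is established.** Net physician time is unknown.
- **That it can be given as a share of intervention cost, borrowing from the earlier trials in B.7.** The cheapest of these, at USD 112 per patient per year, used nurse calls every two months averaging 3.7 minutes, with no home monitor or pharmacist listed. That is a poor base for this arm. The ICER also depends on the between-arm difference, not on total intervention cost.
- **That the time data are already logged.** C.15 promises durations for calls only.

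**What to change.** Replace the sentence in C.20.b and reconcile it with C.9.b, C.9.c and C.13 by stating that:

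1. Study-physician, mid-level substitute and PCP time is costed in both arms, so that shared tasks such as the extreme-BP co-signature are treated alike.
2. Event counts come from the C.15 records of consultations, PCP contacts and pharmacist medication changes. Each event carries recorded minutes, or a number of minutes set before analysis, at VA wage and fringe rates.
3. The ICER without physician time, and over a range of minutes per event, is reported as sensitivity analyses beside those by cost type already planned in D.6.b.

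The cost is a little extra costing work, including either a minutes field in the consultation log or an agreed figure per event. The ICER is likely to be slightly less favourable to the intervention.
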